## Cost Evaluation

*The cost analysis question is: How much does it cost to introduce and run the “My View” programme?*

We will collect costs from the British Refugee Council in April 2022 of delivering the programme from March 2021 until April 2022, and projected costs to June 2022. Costs for set-up (one off) and recurring costs are to be broken down by:

- staff time for delivering therapy as well as case work (proportion of FTE multiplied by salary plus other staff costs such as national insurance contributions),
- any costs associated with recruiting and training therapists,
- any costs related to case work (e.g. staff time, travel costs, use of platforms (Zoom, phone calls), postage and stationary),
- any costs related to group therapy (e.g. equipment)
- any other overheads including facilities (cost of office and venue hire associated with face to face provision) and equipment costs (based on individual needs (own resources of cards, art materials, sleep packs, stress balls, work sheets for example the tree of life or team of leaf, body outlines etc.).

We will estimate a per pilot-site cost (given the differences in volumes) and provide costs per child, per site. We will also ask the British Refugee Council to distinguish between set-up costs and day-to-day running of the programme costs. We could compare the per-child costs with published costs for similar services, such as counselling for children with mental or emotional difficulties.

---

 <https://www.pssru.ac.uk/pub/uc/uc2020/1-services.pdf>

## Risks

Table 7: Risk register

| Risk   | Mitigation  |
|--|---|
| Low participation by young people in My View   | The programme has and will mitigate against this (e.g., understanding cultural competency, well-connected, integrated into existing services). The evaluation will examine adoption and acceptability, including the programme reach and take up as well as the acceptability by participants and staff.
Likelihood: Medium
Impact: High  |
| Difficulty in recruiting young people participants of for interviews   | We are ensuring that the info sheet is translated, and interviews are short and concise.
We are also offering small compensation/ incentives for interviews, and only recruiting for interviews after counselling completion when there will be better trust built up
Likelihood: Low
Impact: Medium   |
| Staff and young people only want to report positive aspects of the service in IPE evaluation   | We will mitigate this through: 
 
● Independence of the evaluation team
 
● Careful discussion of consent processes and anonymity and confidentiality
 
● Use of interpreters where necessary
 
● Use of open questions, probes in semi-structured interviews
 
 Sensitively approaching data collection
Likelihood: High
Impact: Medium |
| Difficulties in carrying out My View as designed and planned by programme team (e.g., staff illness/turnover, Covid-19 regulations changing or recruitment under remote conditions, or other administrative barriers). | The programme has and will mitigate against this (e.g., virtual design, well-connected, integrated into existing services)

The IPE will capture the appropriateness of the service (including fit with professional/service norms) and the feasibility of the implementation, facilitators and barriers to implementation, and implementation strategies.
Likelihood: Low
Impact: High             |
| Unrealistic expectations by funder, programme, and/or partners on ability to detect impact and change  | We will mitigate this through: 
 
● Clear communication
 
● Strong working relationships
 
● Build-up knowledge to detect impact in future evaluations
 
 Sound design, measures, and understanding of the importance of randomisation
Likelihood: Very low
Impact: Low   |
| Findings not applicable to future delivery in non-Covid-19 circumstances   | One basis of the evaluation is that there is value in exploring online delivery of services and that many services will continue online for young people who are remote / young people more confident with technology. Efforts will be made to distinguish features of programme delivery and implementation that might vary in non-Covid-19 circumstances.
Likelihood: Low/ Medium
Impact: Low / Medium  |

|  |  |
|--|--|
| Quality of the data collected by My View/British Refugee Council makes it difficult to detect impact | Therapeutic staff trained by My View programme managers. Importance of data collection re-iterated by workshop with evaluators. Baseline data to be scrutinised and additional training offered if necessary.
Likelihood: Low/Medium
Impact: High  |
| Young people drop out and no post-data can be collected  | Tracking of young person through referrer by therapist. Session 6 data collection to be used as fall-back.
Likelihood: Medium
Impact: High   |
| Difficulty collecting data from the control group  | Waitlist design means we can get accurate 'pre' recording. Monthly check-in by therapist or BRC admin with young people while on waitlist
Likelihood: Low / Medium
Impact: High  |
| Contamination / crossover between the treatment and control groups                                   | It is possible that young people assigned to the control group receive the treatment. This might be when a decision has been made to override randomisation in high-risk cases. It may also take place if, for example, a young person in the control group attends a drop-in group session (e.g. at the Kent Reception Centre). In both cases, this will be recorded so the evaluation will be aware of how often this happens, and if appropriate, undertake sensitivity analysis (e.g. conducting analysis with and without these individuals to detect any differential impact).
Likelihood: Medium
Impact: Medium |
| Timetable / delivery delays if therapists take longer than expected to recruit                       | Full complement of therapists currently recruited.
Likelihood: Low / Medium
Impact: Low / Medium   |
| Early data collection finds negative outcomes for intervention group young people                    | As the programme is established and has been run before, this is unlikely to happen. This will be discussed as part of the ethics process.
Likelihood: Very low
Impact: Low  |

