## Outcome Measures

### Primary outcome measure

The primary outcome measurement is the Young Person's Clinical Outcomes in Routine Evaluation (YP-CORE) measure. The YP-CORE is a measure of psychological distress and is widely used in mental health and school counselling services. It is freely available to use.

The baseline YP-CORE measurement will take place at the pre-assessment session for young people randomised i.e. both the treatment and control groups. Data will then be collected at the following timepoints:

- Treatment group:
  - Baseline at the pre-assessment session
  - After six My View sessions (midpoint)
  - After three months of My View (endline / post-treatment)
- Waitlist control group:
  - Baseline at the pre-assessment session
  - After three months of being on the waitlist (endline) – this will be at a second pre-assessment session before the young person starts My View
  - After six My View sessions (standard practice, not included in the evaluation)
  - After three months of My View (standard practice, not included in the evaluation).

---

 We have used 47 cases per block as an approximation to the 280 total required (i.e.  $47 \times 6 = 282$ ).

 <https://www.ncbi.nlm.nih.gov/pmc/articles/PMC6860299/>

 <https://www.corc.uk.net/outcome-experience-measures/core-measurement-tools/>

 If, for any reason, the midpoint questionnaire (after 6 sessions) gets delayed and therefore becomes close to the endline questionnaire (to be completed after three months), therapists may decide to only collect the endline.

The measure is brief, with just 10 items covering anxiety, depression, trauma, physical problems, functioning and risk to self. As such, this covers the following short-term outcomes included in the programme's theory of change:

- Psychological and emotional well-being
- Emotional self-regulation
- Safety and risk of harm

For each item, the respondent selects one response to indicate how they have been feeling over the last week:

- Not at all
- Only occasionally
- Sometimes
- Often
- Most or all of the time

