## Missing Data

We anticipate that the baseline YP CORE questionnaire will be completed by all at the initial assessment interview, given the importance of the baseline in the analysis anyone not completing will be excluded from the analysis. Similarly, we anticipate the questionnaire measures of secondary outcomes to be collected at that same time. The endline primary outcome measures will be collected three months after starting the intervention with attempts

---

made to collect intermediate YP-CORE scores at the 6-week interval (for the treatment group only).

We anticipate that the key risks to missing data will arise with the endline outcome score. Cases without an endline score will not be imputed and will be dropped from the analysis, which will be run using complete case response data only. BRC routinely attempt to collect YP-CORE data after the first six weeks but only for the treatment group. Consequently, we cannot treat both groups equally with respect to missing endline data, so will not attempt to use the 6-weekly score for imputation purposes.

If there is evidence of differential attrition between the treatment and control groups in terms of socio-demographic characteristics, we will construct a weight to account for differential attrition and include a weighted version of the primary and secondary outcomes in the sensitivity analysis to check on the stability of the impact estimate.

If there is no evidence of differential attrition, no weighting will be undertaken.

It is possible, however considered highly unlikely, that young people may give partial responses to the baseline and/or outcome data and, if this occurs, item responses may be imputed to enable a more complete summary score.

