### **My View may stir up issues meaning outcomes get worse before they get better**

As with any therapeutic intervention, engaging in My View may bring up traumatic past experiences, which may make young people feel worse during the intervention before they start working through these experiences and start feeling better. As there is limited time available in this evaluation, some young people may only be part-way through the intervention when the post-measure is collected. Similarly, some young people may only have attended a small number of group sessions within the three months of the evaluation observation period. If data allow, we will explore statistically any trends in changes in outcomes during the available time period in relation to number of sessions attended. This will include any data collected in Session 6.

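### The risk register offers session 6 scores as a fall-back for missing endlines, which the Missing Data section rules out because only the treatment arm has them

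*Protocol*

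**What the plan says.** **Missing Data section.** The primary analysis uses complete cases: "Cases without an endline score will not be imputed and will be dropped from the analysis". The section considers the mid-treatment YP-CORE and rejects it. It notes that "BRC routinely attempt to collect YP-CORE data after the first six weeks but only for the treatment group", concludes that "we cannot treat both groups equally with respect to missing endline data", and closes the matter: "so will not attempt to use the 6-weekly score for imputation purposes".

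**Risks, Table 7.** For the risk "Young people drop out and no post-data can be collected", rated medium likelihood and high impact, the mitigation is tracking through the referrer, followed by "Session 6 data collection to be used as fall-back".

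**Primary outcome measure section.** The treatment group is measured at baseline, after six sessions and at three months. The control group's six-session score is taken only after its 3-month endline, once it has started My View, and is marked as outside the evaluation. A footnote lets therapists skip a delayed midpoint when it would fall close to the endline.

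**Ethics, on outcomes getting worse before they get better.** Therapy may stir up past experiences, "which may make young people feel worse during the intervention before they start working through these experiences". The same paragraph plans, if data allow, to explore outcome trends by number of sessions attended, including session 6 data.

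**The concern.** Both instructions address the same event, a missing endline score, and they give opposite answers. One removes the case. The other, taken at its word, keeps it with a substitute score.

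The substitute can exist in one arm only. Under the fall-back, a treatment-arm dropout could stay in the analysis with a score taken part-way through therapy, while a control-arm dropout would be lost. Retention and outcome timing would then differ by arm. The trial is not blinded and therapists collect the scores, so a choice between two written rules could also be made with knowledge of the results. The Missing Data section itself gives unequal treatment of the groups as its reason for not using the score.

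There is also a minor inconsistency in describing the midpoint. The Primary outcome measure section and the risk register count six sessions, while the Missing Data section counts six weeks. The Activities section says that missed appointments stretch the course beyond 12 weeks, so the two need not coincide.

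**Working it through.** The contradiction is textual and needs no arithmetic. The figures below show only what would be at stake.

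**1. The plan's own figure.** Inputs from the sample size section: R² = 0.5, two-sided alpha 0.05, power 0.8, 6 strata averaging 47 cases, and 145 v 135 allocated. With 6 × 47 = 282 cases split evenly and 269 degrees of freedom:

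MDES = (t₀.₉₇₅ + t₀.₈₀) × √[(1 − R²) / (P(1 − P) × 282)] = 2.812 × √[0.5 / (0.25 × 282)] = 0.237.

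The normal approximation at 145 v 135 gives 2.802 × √[0.5 × (1/145 + 1/135)] = 0.237. Both round to the stated 0.24. With the illustrative SD of 7.6, the detectable difference is 0.24 × 7.6 = 1.824 points, which the protocol gives as 1.8.

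**2. Who would be analysed (assumption: equal loss of 10%, 20% or 30% in each arm).**

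| Loss | Complete cases | Fall-back, upper bound | Treatment-arm scores filled |
|---|---|---|---|
| 10% | about 130 v 122 | 145 v 122 | about 14 |
| 20% | 116 v 108 | 145 v 108 | 29 |
| 30% | about 102 v 94 | 145 v 94 | about 44 |

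The fall-back column assumes that every treatment-arm dropout has a session 6 score. Those who leave before session 6, or whose midpoint was skipped, have none.

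**3. Shift in the treatment-arm mean.** Shift = proportion filled × gap between the session 6 score and the unseen endline (gap assumed to be 1 to 3 points).

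- Smallest: 0.10 × 1 = 0.1 points, or 0.1/1.824 = 5% of the detectable difference.
- Central: 0.20 × 2 = 0.4 points, or 22%.
- Largest: 0.30 × 3 = 0.9 points, or 49%.

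**4. Power against a true 1.824-point effect, at 20% loss.** Residual SD = 7.6 × √0.5 = 5.374. SE = 5.374 × √(1/n_T + 1/n_C). Power = Φ(effect/SE − 1.96). Dropout is taken as unrelated to outcome, and session 6 scores as having the same residual SD.

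Under the fall-back, the expected difference depends on what session 6 shows:

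- Half the effect: 1.824 − 0.20 × 0.5 × 1.824 = 1.642.
- Scores 2 points worse than the endline: 1.824 − 0.20 × 2 = 1.424.

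| Rule and scenario | Loss in treatment arm only | Loss in both arms |
|---|---|---|
| Complete cases | 116 v 135, SE 0.680: 76% | 116 v 108, SE 0.719: 72% |
| Fall-back, half the effect | 145 v 135, SE 0.643: 72% | 145 v 108, SE 0.683: 67% |
| Fall-back, 2 points worse | 145 v 135, SE 0.643: 60% | 145 v 108, SE 0.683: 55% |

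The fair comparison is with complete cases at the same loss. Power with all 280 endlines observed is 81%, but that is not what the Missing Data rule would deliver once endlines are missing. Against complete cases, the fall-back costs about 4 to 5 percentage points if session 6 shows half the effect, and about 16 to 17 if its scores are 2 points worse.

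**The case against.** The strongest reply is that the register entry is one terse cell in a project-management table. It does not mention the primary analysis, imputation or substitution. The Missing Data section is the analysis rule: it names the mid-treatment score, rejects it and gives the reason. An analyst would probably follow it. The ethics section also gives session 6 data an exploratory role, and the fall-back could be meant in that sense. This stands as a limit on the consequence. It does not remove the conflict, because the cell offers session 6 data as the remedy for absent post-data and does not confine it to exploratory work.

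A reader might infer that the protocol commits the primary analysis to one-arm substitution. It does not; that follows only if the register entry is acted on.

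A reader might also infer that session 6 scores are known to be biased upwards against the 3-month score. The protocol does not show this. Its warning concerns feeling worse at any time during the intervention, and it adds that some young people will be only part-way through at the 3-month measure, so the endline may be affected too. The direction of any shift is therefore open.

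The illustrative inputs lean to the unfavourable side: every dropout is assumed to have a session 6 score, and the 1-to-3-point gap has no source in the protocol. The wording of the midpoint is a small matter, since most clients are expected to attend weekly and both phrases refer to the same mid-treatment measurement.

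**Conclusion.** The concern holds as a contradiction between the Missing Data section and the risk register over what happens when the primary endline is missing. The protocol rates that risk as medium likelihood and high impact, so the event is not remote. If the register were followed, the outcome would be filled in the treatment arm alone, for the reason the Missing Data section itself gives against doing so.

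The size is conditional. It rests on assumed attrition, an assumed gap between session 6 and endline scores, and the illustrative SD of 7.6. Within those assumptions the possible shift runs from negligible to about half of the detectable difference. These figures are not predictions. The case for correcting the text is that the correction is nearly free and leaves a single rule in place before results are seen.

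**What to change.** - In Table 7, delete the fall-back sentence, or limit it expressly to the exploratory analysis by sessions attended or to a labelled sensitivity analysis. The Missing Data section should then be the only rule for the primary and secondary analyses. An outright ban on any use of the mid-treatment score is not needed.
- State that the attempt to obtain the 3-month questionnaire from those who stop attending is the same in both arms. The register already lists tracking through the referrer and monthly check-ins for the waitlist, so this mainly aligns existing effort.
- Describe the midpoint in one way in the Primary outcome measure section, the Missing Data section and Table 7.

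The cost is a few words. The downside is that a few treatment-arm endlines count as missing, which the Missing Data section already accepts.

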## Ethics & Participation

We will obtain (to be updated once obtained) research ethics approval through Ipsos MORI's research ethics process in May 2021. The ethics committee will be independent and not otherwise involved in any evaluation activities. If any changes occur to the intervention delivery or evaluation, the Principal Investigator will make these known to the chair of the Ipsos MORI Public Affairs Research Ethics Committee.

### Ethical considerations

In conversation with the British Refugee Council and What Works for Children's Social Care, we have considered ethical risks and trade-offs, and are satisfied that these are sufficient and reasonable. We also believe that the evaluation has merit in providing evidence on the effectiveness of My View as a therapeutic intervention for UASC.

### Consent

#### Administrative data collection and analysis

We will not seek consent to randomisation from UASC. We plan to send therapists an information sheet for them to distribute to their clients who are randomised and those on the waitlist, at initial assessment. This will give young people an opportunity to opt out of their data being analysed for the evaluation (any opt out received will be treated as a request to also not be approached for a qualitative interview).

#### Interviews with therapists, trainers and other staff

We will approach staff via email, having received contact details from the British Refugee Council programme managers. We will provide an electronic copy of our information sheet and consent form. We will check and record whether interviewees consent before starting each interview.

#### Interviews with young people

We will approach young people via their therapists and will provide a translated copy of our information sheet (which will be young people friendly) and consent form. Before the interview we will ensure that young people have understood the information, had the possibility to have their questions answered and seek informed consent.

### Participation

We will learn about any special arrangements or alternative formats from therapists (via Refugee Council programme managers) at the interview selection stage. We will make arrangements to translate information sheets and consent forms, to provide an interpreter, or arrange other support to enable interviews to take place.

### Ethical considerations relating to the RCT

#### The use of randomisation is justified in this context

Previous evaluation of My View has not employed a robust comparison (a counterfactual), which means that we cannot be confident about causality when claims about positive impacts are made. We are in 'equipoise' meaning we are agnostic on whether the

programme is effective or not, making an RCT the logical next step, taking the evidence to the next level.

Well-planned and executed RCTs can establish that programmes lead to particular benefits for UASC, rather than other factors explaining changes. This evaluation therefore has the potential to provide the highest quality evidence to help inform future commissioning and practice.

The randomisation has been designed so as to exclude UASC who are deemed as requiring 'crisis intervention'. After the initial one to three sessions of crisis intervention, young people will not be returned to the waitlist, however, they will continue to receive treatment (if they so wish, in line with therapists' availability) immediately.

Further, at initial assessment, if a young person has been randomised to the waitlist group and the therapists believes them to require crisis intervention, the random allocation can be overwritten.

### **Taking part in the intervention is voluntary**

We will collect data and report on whether young people attend the My View therapy sessions they are offered (as part of the intention-to-treat analysis). Young people have the option to decline the offer to take part in the intervention.

### **Young people in the control group (waitlist) will receive business as usual support**

Young people who are randomised to be on the waitlist will receive business as usual support. This support may vary depending on their location / local authority, the source of the referral and whether any other support can be provided. Due to the waitlist design, young people in the control group will be offered the intervention three months after the randomisation.

